### 10.5.2 Solicited AEs

Solicited local AEs (injection site pain, redness, swelling and itching) and solicited systemic AEs (chills, fever, nausea/vomiting, diarrhea, headache, fatigue, myalgia and arthralgia) will be collected on the day of vaccination and the following 7 days for dose 1, dose 2 and booster dose on a specific diary and after that together with all AEs occurring throughout the trial.

The severity and relatedness for each separate solicited AE should be assessed by the investigator and recorded on the AE form in the eCRF. The severity will be assessed for each day and the relatedness will be assessed overall.

The investigator's assessments on the CRF for severity assessment will be used.

Relatedness will be set to related for solicited local AEs on day 1 to 8 with a non-missing grade > 0 even if it was assessed as not related by the investigator.

For solicited systemic AEs the assessment of relatedness by the investigator will be used for all AEs on day 1 to 8 with a non-missing grade > 0.

Relatedness will be set to missing for all solicited AEs on day 1 to 8 with a missing grade or grade 0.

In case there are more than one solicited AE with the same relationship to study vaccine on a specific day with the same type of reaction (e.g. myalgia, injection site pain, nausea/vomiting) but recorded as different events, records will be collapsed for that specific diary day. Thereby, if there are overlapping events with the same relationship on a given diary day, they will be collapsed and reported with the highest severity grade on that day. Overlapping events with different relationship to study vaccine will not be collapsed.

Solicited events reported as “Nausea” and “Vomiting” are considered to be of the same reaction type “Nausea/Vomiting”.

**Table 5      Intensity Grading\* for Solicited Local Adverse Event**

AE	Grade	Definition
Pain at injection site	0	Absent
	1	Does not interfere with activity
	2	Interferes with activity and/or repeated use of non-narcotic pain reliever >24 hours
	3	Prevents daily activity and/or repeated use of narcotic pain reliever
Redness	0	<2.5 cm
	1	2.5 – 5 cm
	2	5.1 – 10 cm
	3	>10 cm
Swelling	0	<2.5 cm
	1	2.5 – 5 cm and does not interfere with activity
	2	5.1 – 10 cm or interferes with activity
	3	>10 cm or prevents daily activity
Itching	0	Absent
	1	Mild, no interference with normal activity
	2	Moderate, some interference with normal activity
	3	Significant, prevents normal activity

\*FDA toxicity grading scale [1].

**Table 6 Intensity Grading\* for Solicited Systemic Adverse Events**

Adverse Event	Grade	Definition
Fever	0	<38°C
	1	≥38 – 38.4°C
	2	≥38.5 – 38.9°C
	3	≥39°C
Headache	0	Absent
	1	Mild, no interference with normal activity
	2	Moderate, some interference with normal activity and/or repeated use of non-narcotic pain reliever >24 hours
	3	Significant; any use of narcotic pain reliever and/or prevents daily activity
Fatigue	0	Absent
	1	Mild, no interference with normal activity
	2	Moderate, some interference with normal activity
	3	Significant, prevents normal activity
Chills	0	Absent
	1	Mild, no interference with normal activity
	2	Moderate, some interference with normal activity
	3	Significant, prevents normal activity
Myalgia	0	Absent
	1	Mild, no interference with normal activity
	2	Moderate, some interference with normal activity
	3	Significant, prevents normal activity
Arthralgia	0	Absent
	1	Mild, no interference with normal activity
	2	Moderate, some interference with normal activity
	3	Significant, prevents normal activity
Nausea/ Vomiting	0	Absent
	1	Mild, no interference with activity and/or 1 – 2 episodes/ 24 hours
	2	Moderate, some interference with activity and/or >2 episodes/ 24 hours
	3	Significant, prevents daily activity, requires outpatient IV hydration
Diarrhea	0	Absent
	1	2 – 3 loose stools or <400 g/24 hours
	2	4 – 5 stools or 400 – 800 g/24 hours
	3	6 or more watery stools or >800 g/24 hours or requires outpatient IV hydration

\*FDA toxicity grading scale [1]; IV = Intravenous.

### 10.5.3 Unsolicited Adverse Events

Unsolicited AEs occurring on the day of vaccination and the following 28 days will be collected. For unsolicited AEs occurring on the day of dose 2 and the booster dose the following rule will be used:

If the AE is occurring on the day of dose 2 but before vaccination the AE will be presented with AEs for dose 1, if the AE is occurring on day of dose 2 but on or after vaccination it will be presented with AEs for dose 2. If this rule cannot be applied (for example, if the start time of the AE is missing) but the AE occurred on the day of vaccination for dose 2 it will be presented with the AEs for dose 2. The same rule applies for any unsolicited AE occurring on the day of the booster dose.

#### 10.5.4 Serious Adverse Events

SAEs are defined as any untoward medical occurrence that results in death, is life-threatening, requires inpatient hospitalization or prolongation of existing hospitalization, results in persistent disability/incapacity, is a congenital anomaly/birth defect in the offspring of the subject, or is an important medical event.

SAEs and AEs leading to vaccine withdrawal or trial discontinuation will be collected throughout the trial. Non-serious intercurrent medical conditions that may affect the immune response to vaccination will also be collected throughout the trial.

#### 10.5.5 Adverse Events of Special Interest

The following events will be considered as AESI during this trial:

- AEs with a suspected immune-mediated etiology (pIMDs, see Appendix 1),
- COVID-19 disease,
- other AEs relevant to SARS-CoV-2 vaccine development or the target disease (see Appendix 2).

AESIs will be collected on eCRF throughout the trial

#### 10.5.6 Medically Attended Adverse Events

Medically attended AEs will be collected on the eCRF throughout the trial.

#### 10.5.7 Duration Solicited Adverse Events

Duration of solicited local and systemic adverse events are defined as the sum consecutive days with local/systemic adverse events (days 1 to 8) for the same grade. For example, fatigue with grade 1 occurring on day 2 and 3 and day 7 will be counted as two separate events with the duration 2 days and 1 day. For the duration of solicited local and systemic AEs ongoing beyond Day 8 the following definition is used:

If the AE is present on day 8 in the diary and the same AE is present on day 9 on the eCRF, the sum of days between the date of day 9 and end date for the AE on the eCRF is added to the consecutive days as collected on the diary. If the duration of any AE continues after the next dose and the subject experiences an AE of the same type after the second dose, or booster dose, these two events will be presented separately.

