9.1 Safety Assessments

9.1.1 Adverse Events

Definitions of AEs/SAEs, procedures for recording, evaluating, follow-up, and reporting of AEs/SAEs/pregnancy/overdose, as well as assessments of intensity and causality of AEs, are provided in Appendix 10.

Unscheduled visits will be performed when deemed necessary for safety assessments or to ensure data integrity.

Subjects with any Grade 3 solicited or unsolicited AEs reported electronically by the subject will be contacted by the Investigator, and subjects who did not enter any diary information will be prompted and then contacted in case of non-response within 24 hours.

9.1.1.1 **Solicited Adverse Events**

Solicited local AEs (injection site pain, redness, swelling, and itching) and solicited systemic AEs (fever, headache, fatigue, chills, myalgia, arthralgia, nausea/vomiting, and diarrhea) will be recorded on the day of vaccination and the following 7 days using a diary (electronic or paper).

Temperature should be measured orally.

Solicited AEs will be assessed on an intensity scale of absent, mild, moderate, and severe (Table 3 and Table 4). In case of related Grade 3 solicited or unsolicited AEs reported for more than 1 day in the diary, the subject will be questioned to establish the total duration of the AE as exactly as possible and this information will be recorded in the eCRF.

Solicited systemic Grade 3 AEs and unsolicited Grade 3 AEs, except for solicited injection site reactions, must be reported to the medical monitor without delay, on the same day of awareness by the site.

By definition, all local solicited AEs are considered related to trial vaccination. For solicited systemic AEs, the Investigator will assess the relationship between trial vaccine and each occurrence of each AE.

Table 3 Intensity Grading for Solicited Local Adverse Events

AE	Grade	Definition
Pain at injection site	0	Absent
	1	Does not interfere with activity
	2	Interferes with activity and/or repeated use of non-narcotic pain reliever >24 hours
	3	Prevents daily activity and/or repeated use of narcotic pain reliever
Redness	0	<2.5 cm
	1	2.5 – 5 cm
	2	5.1 – 10 cm
	3	>10 cm
Swelling	0	<2.5 cm
	1	2.5 – 5 cm and does not interfere with activity
	2	5.1 – 10 cm or interferes with activity
	3	>10 cm or prevents daily activity
Itching	0	Absent
	1	Mild, no interference with activity
	2	Moderate, some interference with activity
	3	Significant, prevents activity

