10.3.5 Primary Analysis

10.3.5.1 Primary Safety Analysis

The safety measurements will include:

1. AEs (type, intensity, frequency and relationship to trial vaccination), i.e., incidence and severity of AEs for both solicited local (injection site pain, redness, swelling, and itching) and solicited systemic events (fever, headache, fatigue, chills, myalgia, arthralgia, nausea/vomiting, and diarrhea) occurring on the day of vaccination and the

following 7 days) and unsolicited events (occurring on the day of vaccination and the following 28 days).

2. SAEs and AESIs throughout the trial.

Solicited AEs: For reactogenicity assessment, for each dose level and dose in each phase, the number and percentage of subjects with at least 1 solicited AE of any kind, by severity grade, for local, systemic, and overall, will be summarized after the first vaccination, after the second vaccination, after the booster vaccination (if applicable), and after any vaccination. In addition, results from the expansion phase will be tabulated by group. For subjects with more than 1 episode of the same event, the maximum severity will be used for tabulations. In addition, for each dose level and dose in the dose escalation and expansion phases, the frequencies and severity of each solicited AE will be summarized for each vaccination day and the following 7 days. Similar tabulations will be performed for solicited systemic AEs considered as related to the trial vaccine. The duration and severity of solicited AEs will be analyzed at subject level.

In addition, other indicators of safety (e.g., body temperature) will be collected and summarized. The number and percentage of subjects with Grade 3 adverse reaction(s) or SAEs considered as related to the trial vaccine according to the Investigator with the 95% credibility interval based on the Beta (0.5,0.5) prior distribution for each dose level and dose will be calculated and summarized.

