### 10.5.1 Treatment Emergent Adverse Events (TEAE)

A TEAE is any AE that first occurs or increases in severity or relationship to trial vaccine after the first dose of vaccine. AEs which change in severity or relationship to trial vaccine are assigned a new start date and captured as a new record in the CRF. Hence, an AE is defined as TEAEs if the start date/time is after the date/time of first vaccination. Imputed AE start date/time as defined in Section 10.3 will be considered when assessing if an AE is treatment emergent. If the AE start date is still missing after applying imputation rules (i.e. missing year), the AE will be considered treatment emergent.

All solicited AEs are considered treatment emergent, even in the case that (partially) missing or conflicting date/time information is recorded or imputed.

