## 12.8.2 Analysis Solicited AEs

The following summaries of solicited AEs within 7 days after each trial vaccination and within 7 days after any trial vaccination will be provided:

- Summary of solicited AEs, local AEs and systemic AEs, overall and by maximum grade
  - will also be presented by sex (female/male) for any dose, dose 1, dose 2 and booster dose regardless of retrospective serology status at baseline.
- Occurrence of local AEs, overall and by maximum grade
- Occurrence of systemic AEs, overall and by maximum grade
- Occurrence of related systemic AEs, overall and by maximum grade (mild / moderate / severe)
- Duration (days) of solicited AEs, overall and for grade 3 events
- Duration (days) of local AEs, overall and for grade 3 events
- Duration (days) of systemic AEs, overall and for grade 3 events
- Duration (days) of related systemic AEs, overall and for grade 3 events
- Daily summary of local AEs (only for each dose)
- Daily summary of systemic AEs (only for each dose)
- Daily summary of related systemic AEs (only for each dose)
- Summary of time of onset (Day) for grade 3 solicited AEs, any solicited AEs, local, systemic AEs, and related systemic AEs
- Time of onset (Day) of local AEs
- Time of onset (Day) of systemic AEs
- Time of onset (Day) of related systemic AEs
- Number and percentage of subjects with solicited Grade 3 adverse reaction(s) or SAEs considered as related to the trial vaccine according to the Investigator with the 95% credibility interval based on the Beta (0.5, 0.5) prior distribution for each dose level and dose will be calculated and summarized.
- Individual solicited local and systemic adverse events will be displayed in by-subject figures
- Individual grade 3 solicited local and systemic adverse events will be presented in a figure.

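### SAP 10.5.7 measures solicited-AE duration in same-grade runs, so an unbroken reaction splits at each grade change and mean overall duration can be shortened

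*SAP*

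**What the plan says.** SAP 10.5.7 defines the duration of solicited local and systemic events as "the sum consecutive days with local/systemic adverse events (days 1 to 8) for the same grade". Its one worked example is fatigue at Grade 1 on days 2, 3 and 7, which "will be counted as two separate events with the duration 2 days and 1 day". For reactions that outlast Day 8, it adds the eCRF days from day 9 to the diary days.

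SAP 10.5.2 says of solicited events: "The severity will be assessed for each day and the relatedness will be assessed overall". Its collapsing rule covers overlapping records of one reaction type with the same relationship on a given diary day: "they will be collapsed and reported with the highest severity grade on that day". SAP 10.5.1 says "AEs which change in severity or relationship to trial vaccine are assigned a new start date and captured as a new record".

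The outputs that use duration are in two places. SAP 12.8.2 lists "Duration (days) of solicited AEs, overall and for grade 3 events", with parallel lines for local, systemic and related systemic events. SAP 9.4 asks for mean and SD of duration by group under the primary safety endpoints, and again for the booster under the secondary ones. Protocol 10.3.5.1 adds: "The duration and severity of solicited AEs will be analyzed at subject level".

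**The concern.** The time a subject has a reaction and the time a subject spends at one grade of it are different quantities. The definition in SAP 10.5.7 measures the second, and it is the only definition available for tables that are meant, at least in part, to report the first. With daily grading, a reaction that builds and fades is cut at each change of grade.

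Duration is part of the primary safety endpoints. If same-grade runs enter the mean as separate events, two groups whose reactions last equally long can show different means only because grades change more often in one of them. The planned sensitivity analysis in SAP 10.3 would not reveal this, because it concerns missing or partial dates. Two programmers working carefully from the same text could also produce different tables.

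**Working it through.** **1. The SAP's own example.** Grade 1 on days 2, 3 and 7.
- Run ends at a symptom-free day or a grade change (literal rule): 2 days and 1 day.
- Run ends only at a symptom-free day (any-grade rule): 2 days and 1 day.

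Both reproduce the SAP's figures. The example holds the grade constant, so it cannot show what happens when the grade changes. It does show that two runs in one subject are counted separately and not added to 3.

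**2. Unbroken reactions with a grade change (assumed diaries).**

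| Daily grades | Literal runs | Mean of runs | Any-grade run |
|---|---|---|---|
| 1-1-1 | 3 | 3 | 3 |
| 1-2-1 | 1, 1, 1 | 1 | 3 |
| 2-2-1-1 | 2, 2 | 2 | 4 |
| 1-2-2-1 | 1, 2, 1 | 4/3 = 1.33 | 4 |

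The literal runs always add up to the any-grade length (1 + 2 + 1 = 4). Splitting leaves total days unchanged and can only raise the number of runs, so a per-run mean can fall or stay the same but cannot rise.

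**3. Does any text rejoin the parts?**
- The collapsing rule in SAP 10.5.2 works within a diary day, not across days.
- The day-9 rule in SAP 10.5.7 adds later days but does not join earlier parts. Example: Grade 2 on days 6 and 7, Grade 1 on day 8, eCRF record for days 9 to 11 (3 days, counted inclusively). Literal parts are 2 and 1 + 3 = 4, mean 3; the reaction lasted 6 days.
- After Day 8 a severity change opens a new eCRF record (SAP 10.5.1), and nothing says successive records are joined.
- SAP 12.8.2 names an overall duration but gives it no derivation of its own.
- Protocol 10.3.5.1 sets the subject as the level of analysis, but neither document says how several runs in one subject are combined.

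**4. How large could it be?** The documents give no grade paths, so these inputs are assumptions: one reaction per subject, each truly lasting 3 days, and a fraction f changing grade either once (such as 1-2-2, runs 1 and 2) or twice (1-2-1, runs 1, 1 and 1).

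| Summary | Formula | f = 10% | 25% | 50% |
|---|---|---|---|---|
| Per event, one change | 3/(1+f) | 2.73 | 2.40 | 2.00 |
| Per event, two changes | 3/(1+2f) | 2.50 | 2.00 | 1.50 |
| Per subject, longest run, one change | 3−f | 2.90 | 2.75 | 2.50 |
| Per subject, longest run, two changes | 3−2f | 2.80 | 2.50 | 2.00 |
| Per subject, mean of runs, one change | 3−1.5f | 2.85 | 2.63 | 2.25 |
| Per subject, mean of runs, two changes | 3−2f | 2.80 | 2.50 | 2.00 |
| Per subject, runs summed | 3 | 3.00 | 3.00 | 3.00 |

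The true mean is 3.00 in every cell. The result depends on a combining rule that the SAP does not give.

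**The case against.** The best defence is that the same-grade condition was written for grade-specific tables. SAP 12.8.2 sets overall duration against Grade 3 duration, and overall may well be meant to ignore grade. The day-9 rule refers to the same AE without a grade condition, which also suggests continuity by event. Time spent at Grade 3 is meaningful in its own right: the individual stopping rules (Protocol 5.4.1) turn on how soon a Grade 3 event falls to a lower grade. If runs are summed per subject, the split does no harm. The trial is descriptive, no stopping or dose rule uses mean duration, and the incidence, maximum-grade and daily summaries are unaffected.

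Much of this stands, and it limits the point. It does not remove it, because neither saving reading is written down. The SAP has one definition for both kinds of table, and its example counts runs separately. The estimand's mention of total duration stands beside the solicited period and most naturally refers to days beyond Day 8, not to joining runs of different grade.

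Three stronger readings are tempting but unsupported:
- *The worked example proves splitting at grade changes.* It has one grade and a symptom-free gap.
- *The SAP contradicts the protocol's definition of duration.* Protocol 9.1.1.1 does say that "the subject will be questioned to establish the total duration of the AE as exactly as possible", but this is a data-collection instruction for related Grade 3 events reported on more than one day, not an analysis definition.
- *The reported mean durations are biased.* The documents do not show which derivation was programmed.

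**Conclusion.** The point holds as a defect in a stated rule: followed as written, SAP 10.5.7 gives the wrong quantity for overall duration whenever the grade changes during a reaction. For a mean over separate runs the error is downward or nil. It is nil if grades stay constant, if runs are summed within each subject, or if overall duration is programmed without regard to grade.

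Its size is unknown. The figures in the second table show how the mean behaves under assumed 3-day reactions and assumed shares of grade changes; they do not estimate what this trial's data will show. The conclusion assumes that the target of the overall tables and of the primary safety mean is the length of the reaction. If time at a single grade was intended, the rule is coherent but the outputs should be labelled that way. The consequence is confined to the duration summaries, but these belong to the primary safety endpoints, and the point should be settled before the final analysis.

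**What to change.** In SAP 10.5.7:
- Define overall duration as consecutive days at any grade of 1 or more. After Day 8, join successive eCRF records of the same AE that differ only in severity.
- Keep consecutive Grade 3 days as the duration for the Grade 3 tables only.
- State how several episodes in one subject enter the mean (for example longest, total, or each counted), consistent with the subject-level analysis in Protocol 10.3.5.1.
- Add a worked example with a grade change, such as 1-2-2-1 giving an overall duration of 4 days.
- State which derivation was used in the three interim analyses recorded in SAP 11.1.

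The cost is a few sentences and one changed derivation, with no new data. SAP 6.0 already provides for tracked changes before final database lock. The drawback is that durations reported at the interim analyses may differ from the final ones and may need an explanatory note or a re-run.

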4.2.1 Primary

- The frequencies, intensities, and duration of solicited local AEs on Day 1 and Day 29 and the following 7 days by dose and group.
- The frequencies, intensities, duration, and relationship to trial vaccination of solicited systemic AEs on Day 1 and Day 29 and the following 7 days by dose and group.
- The occurrence, intensities and relationship to trial vaccination of unsolicited AEs on Day 1 and Day 29 and the following 28 days by dose and group.
- The occurrence and relationship to trial vaccination of SAEs and AESIs throughout the trial.

On Day 29 and Day 43:

- The proportion of subjects seroconverting for SARS-CoV-2 spike protein antibodies, as measured by ELISA.

- Individual SARS-CoV-2 spike protein-specific antibody levels in serum, as measured by ELISA.
- Geometric mean titers (GMTs) of serum SARS-CoV-2 spike protein antibodies, as measured by ELISA.
- The proportion of subjects seroconverting for SARS-CoV-2 neutralizing antibodies, as measured by an activity assay.
- Individual SARS-CoV-2 neutralizing antibody levels in serum.
- GMTs of serum SARS-CoV-2 neutralizing antibodies, as measured by an activity assay.

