### 9.4 Estimands

ENDPOINTS (subject level)	ESTIMANDS (population level)
Primary Safety	

The frequencies, intensities, and duration of solicited local AEs on Day 1 and Day 29 and the following 7 days by dose and group.
 
The frequencies, intensities, duration, and relationship to trial vaccination of solicited systemic AEs on Day 1 and Day 29 and the following 7 days by dose and group.
 
The occurrence, intensity and relationship to trial vaccination of unsolicited AEs on each vaccination day and the following 28 days by dose and group.
 
The occurrence and relationship to trial vaccination of SAEs and AESIs throughout the trial.
	
Safety set. Subjects who were unblinded and/or received an authorized/licensed COVID-19 vaccine will be censored at the day after unblinding and/or vaccination receipt.
 
The number and percentage of subjects overall and by dose level:
 
Each solicited local AE within 7 days after each trial vaccination by intensity and overall.
 
Each solicited systemic AE within 7 days after each trial vaccination by intensity, by relationship to trial vaccine and overall.
 
The mean duration in days by group with standard deviation of solicited AEs (within the solicited period, total duration).
 
At least 1 unsolicited AEs, at least 1 grade unsolicited AEs and each unsolicited AEs by SOC/PT occurring within 28 days after each trial vaccination and overall by causal relationship to trial vaccine and overall.
 
At least 1 SAE, or at least 1 AESI to vaccine overall by causal relationship to trial vaccine and overall.

ENDPOINTS (subject level)	ESTIMANDS (population level)
Primary Immunogenicity	

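### Solicited-AE duration: the SAP derives it per run of same-grade days and gives no rule to return to the subject level that the protocol requires

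*SAP*

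**What the plan says.** Duration belongs to the primary safety endpoint. Protocol 4.2.1 lists "The frequencies, intensities, and duration of solicited local AEs on Day 1 and Day 29 and the following 7 days by dose and group", with a parallel item for systemic events. The synopsis and section 10.3.5.1 both set the unit: "The duration and severity of solicited AEs will be analyzed at subject level". Neither says which per-subject summary is meant (total, longest or other).

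SAP 10.5.7 defines duration as the "sum consecutive days with local/systemic adverse events (days 1 to 8) for the same grade". Its example is grade 1 fatigue on days 2, 3 and 7, which "will be counted as two separate events with the duration 2 days and 1 day". An event still present on day 8 and recorded on day 9 has the later days added from the eCRF.

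SAP 9.4 gives the population-level summary: "The mean duration in days by group with standard deviation of solicited AEs (within the solicited period, total duration". The same line appears for the booster under secondary safety. SAP 12.8.2 lists the tables, starting with "Duration (days) of solicited AEs, overall and for grade 3 events", then local, systemic and related systemic events, after each vaccination and after any vaccination. Neither section names the averaging unit or the denominator.

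SAP 6.1 lists two changes from the protocol, on cell-mediated immunity and asymptomatic infection. Duration is not among them.

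**The concern.** The protocol fixes the subject as the unit, and the SAP's derivation produces events. A step is needed to get back to one value per subject, and it is missing. For severity the plan does have such a step: Protocol 10.3.5.1 foresees repeat episodes of the same event and takes the maximum grade. Duration has no counterpart.

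Two features of the derivation split a subject's experience. A symptom-free gap starts a new event. So does a change of grade, because a run is defined within one grade and the text does not confine that condition to the grade 3 rows. If the resulting events are averaged, a subject whose symptom returns, or rises and falls in grade, lowers the mean although that subject was unwell for longer. Subjects with more events also carry more weight. The reported mean, SD and n would then describe events, while a reader of the protocol would take them to describe subjects.

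**Working it through.** **1. The SAP's own example.** Counting runs of consecutive days at the same grade for grade 1 on days 2, 3 and 7 gives runs of 2 and 1, exactly as SAP 10.5.7 states.

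- Event level: n = 2, mean (2 + 1)/2 = 1.5 days, SD 0.71.
- Subject level: n = 1, with a total of 3 days, a longest episode of 2 days, or a mean episode of 1.5 days.

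**2. Change of grade (assumed pattern).** One unbroken 5-day symptom graded 1, 2, 3, 2, 1 has no two adjacent days at the same grade. The rule gives five events of 1 day each: event mean 5/5 = 1 day, against 5 symptom days.

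**3. Two subjects.** Subject A is the SAP example (2 and 1). Subject B has one 5-day episode (assumed).

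| Summary | n | Mean (days) | SD |
|---|---|---|---|
| Events | 3 | (2 + 1 + 5)/3 = 2.67 | 2.08 |
| Subject total | 2 | (3 + 5)/2 = 4.00 | 1.41 |
| Subject longest | 2 | (2 + 5)/2 = 3.50 | 2.12 |
| Subject mean of episodes | 2 | (1.5 + 5)/2 = 3.25 | 2.47 |

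The same diary data give four different means, and the documents do not say which is intended.

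**4. Group level.** The documents do not say how common split episodes are. Assume that a share f of affected subjects has the 2 + 1 day pattern and the rest have one 2-day episode. Per affected subject there are 3f + 2(1 − f) = 2 + f symptom days and 2f + (1 − f) = 1 + f events. So:

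- event mean = (2 + f)/(1 + f)
- mean of subject totals = 2 + f

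| f | Event mean | Mean of subject totals |
|---|---|---|
| 10% | 2.1/1.1 = 1.91 | 2.10 |
| 20% | 2.2/1.2 = 1.83 | 2.20 |
| 30% | 2.3/1.3 = 1.77 | 2.30 |
| 50% | 2.5/1.5 = 1.67 | 2.50 |

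The two summaries move in opposite directions: as more subjects have a recurrence, the subject total rises and the event mean falls. The mean of the longest episode stays at 2.00 throughout.

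**The case against.** The strongest reply is that SAP 10.5.7 defines how long an event lasts and not what the mean is taken over. The endpoint column of SAP 9.4 is headed "ENDPOINTS (subject level" (closing bracket omitted), and the summary line there mentions total duration, so a per-subject total remains possible. This stands in part: averaging over events is the natural reading, but it is not stated. It does not settle the matter. The mean sits in the population-level column, and the mention of total duration may only separate days 1 to 8 from the count that adds days after day 8. If the column heading does mean one value per subject, it conflicts with 10.5.7. Either way, a programmer cannot tell which table to produce.

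A reader might also infer that repeated events from one subject are treated as independent and that chance differences between arms become more likely. The documents do not support this. Protocol section 10 and SAP 12.0 allow descriptive statistics only, and no test, standard error or confidence interval for duration is planned. An SD describes spread and does not shrink as events are added.

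Nor should too much be made of SAP 10.5.2, where "Overlapping events with different relationship to study vaccine will not be collapsed". Local events on days 1 to 8 are all set to related, so the split cannot arise for them. For systemic events, keeping causality apart serves the related-systemic table.

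Finally, the by-subject figures in SAP 12.8.2 show individual solicited events. They help, but they do not define the tabulated mean.

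**Conclusion.** The protocol asks for duration by subject. The SAP derives it by same-grade run, never returns to one value per subject, leaves the unit and n of the mean unstated, and declares no departure. This is more than missing detail, because the rule as written turns 3 symptom days into an event mean of 1.5 days in the SAP's own example.

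The gap between the event mean and the mean of subject totals is 0.19 days at f = 10% (2.10 − 1.91) and 0.53 days at f = 30% (2.30 − 1.77). These figures assume the 2 + 1 pattern, unchanging grades and averaging over events. Grade changes could widen the gap, and if few subjects have split episodes it is small. The protocol does not name total days as the subject-level summary, so that comparison is one choice among several. The consequence is confined to what the descriptive mean, SD and n represent. The correction should be made, since it concerns a primary endpoint and costs little.

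**What to change.** In SAP 10.5.7, 9.4 and 12.8.2:

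- Derive one duration per subject, per symptom and per dose, for example the total days at grade 1 or above on days 1 to 8. Apply the existing after-day-8 rule to obtain total duration.
- State that a change of grade does not end an episode in the overall rows.
- For grade 3 rows, count days at grade 3. For related-systemic rows, count only days with related records.
- For the pooled rows (any solicited, local, systemic), use one value per subject per dose: the number of days with at least one such symptom.
- For the any-dose rows, use one value per subject and state how doses are combined.
- Report n as the number of subjects with the symptom, and keep episode-level durations in the listings.
- If an event-level table is retained, label it as such and declare it in SAP 6.1.

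The cost is SAP wording and one variable re-derived from data already collected. The downside is that separate episodes of a symptom are no longer visible in the summary table and must be read from the listings.
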